Bioinformatics: Reads will be filtered through the Institute of Genome Sciences bioinformatics pipeline [15]. Operational taxonomic units (OTUs) will be defined using the Quantitative Insights Into Microbial Ecology (QIIME) pipeline as sequences with at least 97% identity, rarified (randomly sampled with replacement) to the minimum number of observed OTUs. Using the Ribosomal Data Project Bayesian classifier in QIIME, OTUs will be assigned to phylum, class, order, family, and genus level-taxa, and their relative abundances will be calculated [16]. Additional microbial measures of interest include alpha diversity (Shannon index, Inverse Shannon), beta diversity (UNIFRAC distances), and phylogenetic diversity (whole tree phylogenetic diversity), as measured using QIIME after using rarefaction to account for differences in amplification across fecal samples [16]. In addition, we would like to consider as exposures phylogenetic composition, assessed down to the levels of phylum, family, and genus. Finally, we will use the programs PICRUSt and Lefse to generate metagenomic data and measures of KEGG pathway abundances from phylogenetic profiles [17].

Characterization of immune response

Breast tissue collection: Tissue-based measures of immune response will require formalin-fixed paraffin-embedded tissues from primary tumor samples. After informed consent is

IRB # 204897 Site: UAMS Version 5 06/07/2019

obtained, archival tissue from a pre-treatment biopsy of primary breast tumor, in the form of a FFPE tissue block or pre-cut slides will be requested either from the diagnosing center or from the Tissue Biorepository. *Four* slides will be received or cut from formalin-fixed paraffinembedded tissues from primary tumor samples collected prior to chemotherapy. Slides will be prepared from an FFPE tumor tissue block of at least 5-µm thickness. An H&E slide will be scanned using an Aperio slide scanner and will be used to characterize the sample in terms of tissue composition (cell density, relative abundance of stromal, epithelial, and adipose cells). We will stain slides for T-lymphocytes and microenvironmental cues using antibodies for CD8, CD4, FoxP3, and PDLM1 using standard methods for cell surface markers and intracellular markers as described in the following reference [30].

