The Principal Investigator will carefully monitor study procedures to protect the safety of research subjects, the quality of the data and the integrity of the study. All study subject material will be assigned a unique identifying code or number. Data obtained during the study will be entered into C3PR and OpenClinica located in the UAMS clinical trial management suite. C3PR is a cancer Biomedical Informatics Grid (caBIG®, NCI) application that will keep a list of subjects

IRB # 204897 Site: UAMS Version 5 06/07/2019

enrolled and specific information regarding their enrollment. Data will be entered into OpenClinica through electronic web-based case report forms (CRFs). OpenClinica is a secure open source system for electronic data capture and clinical data management. Data from OpenClinica can be easily extracted for analysis throughout the study.

After informed consent is obtained, the data will be collected, coded with a study ID number, and stored indefinitely.

Data Analysis

Analyses will be conducted according to study aims. As the aims are considered exploratory, P values < 0.05 will be considered statistically significant and no adjustments will be made for multiple comparisons.

Aim 1. To assess the acceptability and feasibility of study procedures.

We will describe numbers and characteristics of women who are 1) screened, 2) eligible, 3) consented, and 4) complete collections for each type of biospecimen. In a brief form which will accompany the fecal sample, we will ask enrolled women specifically about the acceptability of, and logistical difficulties with, the procedures for collection and packaging of the fecal specimen.

Aim 2. To estimate proportions of patients with pathological complete response by host factors, breast cancer subtypes, tumor characteristics, reported gastrointestinal symptoms, and by categorical measures of gut microbial composition, diversity, and metabolic activity.

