We will estimate and compare rates of pCR by each factor using chi-squared tests for crude comparisons and multivariable logistic regression for adjusted comparisons. Factors of interest will include host factors such as age and menopausal status; and tumor characteristics including: intrinsic subtype assessed using clinically indicated measures (ER and PR status, Her2/neu status, and Ki67 positivity); standard clinical prognostic indicators (TNM stage and histologic grade), and subgroups defined using tertiles of all continuous gut microbial measures.

Aim 3. To estimate the associations of pre-treatment gut microbial composition, diversity, and metabolic activity with anticancer immune responses, measured as relative abundance of immune infiltrates in pre- treatment FFPE breast tumor tissues, and as relative abundance of circulating immune cell subtypes (Th1, Th2, Th17, and Treg) in baseline and longitudinal blood samples. Bivariate and covariate-adjusted associations among measures will be evaluated using Spearman's rank test and General Linear Models, respectively.

Aim 4. To estimate associations of the measures of local and systemic immune responses with host factors such as age, BMI, and smoking status, and with measures of the breast microenvironment including mammographic density and benign parenchymal enhancement on breast MRI. Bivariate and covariate-adjusted associations among measures will be evaluated using Spearman's rank test and General Linear Models, respectively.

Power and Sample Size:

Aim 1: If we screen 60 potential participants, we should be able to estimate, with 95%

IRB # 204897 Site: UAMS Version 5 06/07/2019

confidence, the true proportion of this patient population willing to participate in the study with precision of +/- 20%.

Aim 2: If 40 participants are enrolled and complete study measures, and the expected pCR in the category with the greatest risk of mortality is assumed to be 20%, then we will have 47% power to detect a statistically significant trend in rates of pCR across tertiles of microbiome measures if the odds ratio for the highest tertile is 5.0.

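### Aim 2 tests pCR on tertiles of every continuous microbial measure: this costs power where three groups exist, and sparse taxa have no three equal groups

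*Combined protocol and SAP*

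**What the plan says.** - **Data Analysis, Aim 2.** pCR rates are compared by chi-squared tests (crude) and multivariable logistic regression (adjusted). The factors include "subgroups defined using tertiles of all continuous gut microbial measures". No trend test is named, and no analysis of pCR uses a microbial measure as a continuous variable.
- **Microbial DNA assays, Bioinformatics.** The measures include diversity indices and relative abundances after rarefaction, with composition "assessed down to the levels of phylum, family, and genus". There is no rule for zeros, ties, minimum prevalence or presence/absence coding.
- **Power and Sample Size, Aim 2.** The inputs are 40 women with complete measures, 20% pCR in the group at greatest mortality risk, and an odds ratio of 5.0 in the top tertile. The stated result is: "we will have 47% power to detect a statistically significant trend in rates of pCR across tertiles of microbiome measures".
- **Data Analysis, opening paragraph.** "P values < 0.05 will be considered statistically significant and no adjustments will be made for multiple comparisons".
- **Data Analysis, Aim 3.** Microbial measures are related to immune measures by Spearman's rank test and General Linear Models, with no tertiles specified.

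**The concern.** There are two separate problems.

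First, cutting 40 values into groups of 13 or 14 treats all women within a group as having the same exposure. The crude chi-squared test then also ignores the order of the groups. Both lose power in an aim that starts below 50%, although the planned logistic model could take the measure as it stands.

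Second, the rule covers all continuous measures, and a relative abundance can be zero in many women. If more than one third of values are zero, the lower cut point is zero; if more than two thirds are, both cut points are zero. The analyst would then have to improvise a grouping taxon by taxon, with an unadjusted 0.05 threshold. The resulting estimates are meant to help plan a larger study.

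**Working it through.** **Inputs from the plan.** N = 40, so n = 40/3 = 13.33 per tertile. p1 = 0.20, with the greatest-risk category read as the lowest tertile. Odds ratio 5.0 gives odds 0.25 × 5 = 1.25, so p3 = 1.25/2.25 = 0.556. Alpha is 0.05, taken as two-sided because the side is not stated for Aim 2.

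**Assumption.** The middle tertile is not given. A log-linear step gives an odds ratio of √5 = 2.24 and p2 = 0.359. The mean is p̄ = (0.200 + 0.359 + 0.556)/3 = 0.371.

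**1. The stated 47%.** Cochran-Armitage trend test, scores −1, 0, 1, normal approximation:

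- D = n(p3 − p1) = 13.33 × 0.3556 = 4.741
- V0 = 2n p̄(1 − p̄) = 26.67 × 0.2335 = 6.225, square root 2.495
- V1 = n[p1(1 − p1) + p3(1 − p3)] = 13.33 × 0.4069 = 5.426, square root 2.329
- Power = Φ[(4.741 − 1.96 × 2.495)/2.329] = Φ(−0.064) = 47.4%

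The plan's figure reproduces, and it is a figure for three equal tertiles.

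**2. The named chi-squared test on three tertiles (2 df).**

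- Noncentrality = n Σ(p − p̄)² / [p̄(1 − p̄)] = 13.33 × 0.0635/0.2335 = 3.62
- Power against the critical value 5.99 = 38%. Exact enumeration at 13/14/13 gives 37% and simulation 36%.

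**3. The same truth without tertiles.** Let the measure be standard normal with logit(pCR) = −0.598 + 0.766x. This gives tertile means of 20.0%, 35.6% and 55.6%, matching the plan at both ends. For any score s (sums over 40 women):

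- D = Σ(s − s̄)p, V0 = p̄(1 − p̄)Σ(s − s̄)², V1 = Σp(1 − p)(s − s̄)²
- Continuous value: D = 6.356, √V0 = 3.054, √V1 = 2.615, power Φ(0.141) = 55.6%
- Ranks scaled 0 to 1: D = 1.820, √V0 = 0.882, √V1 = 0.787, power Φ(0.117) = 54.7%

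Simulations of 40,000 samples of 40 gave 56–57% for the continuous value and 54–55% for ranks.

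**4. Taxa with zeros.** The share of women without the taxon is an assumed range. The underlying effect is held as in step 3, and values at or below a cut point go to the lower group. Power uses the step 3 formula, with unrounded group sizes.

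| Absent | Groups (whole women) | Tertile trend | Tied ranks | Present/absent |
|---|---|---|---|---|
| up to 33% | equal thirds | 47% | 53% (at 33%) | 33% (at 33%) |
| 40% | 16/11/13 | 47% | 52% | 37% |
| 50% | 20/7/13 | 46% | 50% | 40% |
| 60% | 24/3/13 | 43% | 47% | 41% |
| 67% | 27/13 | 40% | 44% | 40% |
| 80% | 32/8 | 35% | 37% | 35% |
| 90% | 36/4 | 25% | 26% | 25% |

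At p̄ = 0.371 the expected number of pCRs is 0.371 × 7 = 2.6 in a group of 7 and 0.371 × 3 = 1.1 in a group of 3. These are too few for a reliable chi-squared test.

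**The case against.** **The 47% already counts the tertiles.** A reader might infer that tertiling pushes power below the stated 47%. The documents do not support that. The figure is given for a "trend in rates of pCR across tertiles of microbiome measures", and step 1 reproduces it on that basis. For measures with few ties, the trend test delivers what the plan says. The lower 36–38% comes from using an unordered chi-squared test, not from tertile coding as such.

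**The gain depends on the model.** This stands. The 54–57% assumes a logit-linear relation. If the middle tertile behaved like one of the outer ones, enumeration at 13/14/13 puts the 2-df test at 47–51%, so its deficit would mostly vanish. Small-sample detail matters too: the uncorrected trend test enumerated at 13/14/13 gives 53.3%. Enumerating the same test with a common pCR of 37.1% shows a true error rate of 6.7%, so that figure is flattered. The mid-p version gives 46.3%.

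**Sparse taxa.** A reader might also infer that groups collapse for most measures. The documents give no prevalence, and diversity indices should have few ties. Nor must power fall: if carriers have 55.6% pCR and non-carriers 20%, a 20/20 split has 65% power. And above two thirds absent, the collapsed tertiles are simply absent versus present, so the low power there reflects sparsity.

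**The aim asks for categories.** Aim 2 is exploratory and calls for pCR by categorical microbial measures. That is a good reason to keep reporting proportions by tertile, but not to base the test on them.

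**Conclusion.** The point holds in a limited form. Where three equal groups exist, the tertile trend has the stated 47% power and the chi-squared test as named about 36–38%. Ranks or a continuous term would give about 54–57%. This rests on the plan's inputs, a two-sided 0.05 test and a logit-linear relation.

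For a taxon absent in more than one third of women, three equal groups cannot be formed, and the 47% does not describe the analysis. With the underlying effect held fixed, the loss is small up to 50% absent and clear from about 60%. Under that model ranks recover about 4 to 5 points at 40–67% absent and 2 or fewer at 80% and above. Present/absent coding is below the tertile trend at 40–60% absent and identical to it above two thirds. It would be the stronger choice only if carriage itself drives response.

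The change is worth making because it is cheap and keeps the proportions that Aim 2 asks for. It does not make Aim 2 well powered.

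**What to change.** In Data Analysis, Aim 2:

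- Make the crude test a Wilcoxon rank-sum comparison of each microbial measure between women with and without pCR.
- Enter each measure in the logistic model as a continuous score per SD, suitably transformed, or as the rank score for taxa with many zeros.
- Keep pCR proportions by tertile as descriptive estimates where three groups exist. Describe taxa absent in more than two thirds of women as present/absent. For taxa absent in one third to two thirds, do not offer present/absent as an equal alternative to ranks.

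In Power and Sample Size, Aim 2, state that the 47% is for a trend across three equal tertiles.

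The cost is analysis wording only: no new data or visits. The downside is that the continuous term assumes a monotone, logit-linear relation, which 40 women could hardly test, and the rank test is also aimed at monotone differences. The descriptive tertile table remains as a rough check on shape.

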Many chemotherapeutic agents compromise the integrity of the mucosal barrier in the gut, allowing translocation of gram-positive bacteria in secondary lymphoid organs. While this has, until recently, been considered an undesirable side-effect, it may also represent one mechanism by which chemotherapy stimulates an effective anti-cancer immune response. It has been proposed that the priming of Th17 T-cell responses against commensal microbes following disturbance of the gut mucosal barrier facilitates the accumulation of Th1 helper T cells at the site of the tumor, and thus contributes to tumor regression. Gut microbes may also contribute to the efficacy of chemotherapeutic agents through metabolism of the chemotherapeutic agent to its active form. We will test the hypothesis that gut microbial composition can influence immune response to the tumor, resulting in inter-individual differences in the response to anti-cancer therapies. We will also explore how host factors and microenvironmental factors influence the local immune response to the tumor.

We propose the following specific aims:

- 1. To demonstrate feasibility and acceptability of protocol procedures and measures, including in-home collection of a fecal sample, collection of a blood sample by venipuncture, and collection of breast tissue from newly diagnosed breast cancer patients prior to initiation of neoadjuvant breast cancer therapy.
- 2. To estimate rates of gastrointestinal side effects and pathological complete response in women with breast cancer treated with neoadjuvant chemotherapies, by breast cancer subtypes, tumor characteristics, cancer treatment, and by categorical measures of gut microbial composition, diversity, and metabolic activity.
- 3. To estimate the associations of pre-treatment gut microbial composition, diversity, and metabolic activity with anticancer immune responses, measured as relative abundance of immune infiltrates in pre-treatment FFPE breast tumor tissues, and as relative abundance of circulating lymphocytic subtypes (Th1, Th2, Th17, and Treg) in blood samples collected prior to initiation and following completion of neoadjuvant

IRB # 204897 Site: UAMS Version 5 06/07/2019

chemotherapy.

4. To estimate associations of local and systemic immune responses with host factors such as age, BMI, and smoking status, and with measures of the breast microenvironment including mammographic density and benign parenchymal enhancement on breast MRI.

Study Population

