Blood sample collection: A sample of not more than 30 mL or approximately 6 teaspoons (three 10-mL yellow ACD tubes) will be taken by venipuncture in order to obtain peripheral blood leukocytes. This will be done twice, prior to the initiation, and after completion, of chemotherapy. A trained phlebotomist or registered nurse will draw the blood required for clinical and research purposes. This blood sample will be collected in coordination with clinical care to minimize the number of blood draws experienced by participants. It is important that the first sample be obtained prior to the first dose of chemotherapy. For logistical reasons, blood draws should be completed before 2:30 pm Monday-Friday so that the sample can be processed the same day. After collection, the sample should be kept and transported at room temperature.

Delivery to the laboratory: Research staff will pick up specimens from the Cancer Institute Blood Draw or Infusion Centers. Research staff will re-label specimens with a patient identifier, date of the specimen, and name of visit. When a research specimen is collected, designated research staff will be notified to coordinate delivery and processing of the sample at the [name] Laboratory, in Room B532 of Biomedical Building 1, in the Department of Microbiology and Immunology at the University of Arkansas for Medical Sciences.

Processing: Samples will be processed within 24 hours of the blood draw. Peripheral blood mononuclear cells (PBMCs) will be freshly isolated (within 8 h after the blood draw) from EDTA-treated samples using Ficoll-Hypaque gradient separation (Lymphoprep, Axis Shield, Oslo Norway) and washed, following a standard protocol.

Storage: One of the three aliquots will be stored in the Tissue Biorepository at -80°C or lower. Samples will be kept indefinitely. If a sample is deemed unviable at the time of use, the sample will be mixed with bleach and disposed in a sink. All specimen containers (tubes and containers) will be disposed into biohazard red plastic bags according to UAMS Occupational Health & Safety policy. Red bag waste will be picked up by Occupational Health & Safety for final disposal.

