Aim 3 and 4: If we have 20 participants with both tumor infiltrate measures and measures of gut microbial composition, we will have adequate power (β =80%) to detect relationships between the dependent variable (relative abundances of tumor infiltrating lymphocytes and circulating lymphocytes) and the independent variables gut microbial composition, diversity and metabolic activity; host factors, and measures of the tumor microenvironment) at a two-sided α =0.05 significance level, when the true change in the dependent variables is 0.67 standard deviations per one standard deviation change in the independent variables.

Ethical Considerations

This study will be conducted in accordance with all applicable government regulations and University of Arkansas for Medical Sciences research policies and procedures. This protocol and any amendments will be submitted and approved by the UAMS Institutional Review Board (IRB) to conduct the study. In addition, all study personnel must have completed human subject protection training.

The formal consent of each subject, using the IRB-approved consent form, will be obtained before that subject is submitted to any study procedure. All subjects for this study will be provided a consent form describing this study so they can make an informed decision about their participation in this study. The person obtaining consent will thoroughly explain each element of the document and outline the risks and benefits, alternate treatment(s), and requirements of the study.

The consent process will take place in a quiet and private room, and women may take as much time as needed to make a decision about their participation. The privacy of all subjects will be maintained and questions regarding participation will be answered. No coercion or undue influence will be used in the consent process. This consent form must be signed by the subject and the individual obtaining the consent. A copy of the signed consent will be given to the participant, and the informed consent process will be documented in each subject's medical record.

Dissemination of Data

Results of this study may be used for presentations, posters, or publications. The publications will not contain any identifiable information that could be linked to a participant.

References

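### Post-chemotherapy lymphocyte subsets (Aims 3 and 4): the plan does not name the woman's own baseline value as a covariate, so a pre-treatment association can be read as a response to chemotherapy

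*Combined protocol and SAP*

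**What the plan says.** Blood is drawn before and after treatment. The blood sample section states: "This will be done twice, prior to the initiation, and after completion, of chemotherapy". A baseline value is therefore planned for every woman with a post-chemotherapy value.

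The Specific Aims define the circulating outcome for Aim 3 as the relative abundance of four T-cell subsets "in blood samples collected prior to initiation and following completion of neoadjuvant" chemotherapy. Data Analysis, Aim 3 restates the goal, "To estimate the associations of pre-treatment gut microbial composition, diversity, and metabolic activity with anticancer immune responses", and describes the blood outcome as measured "in baseline and longitudinal blood samples". The method is one sentence, repeated for Aim 4: "Bivariate and covariate-adjusted associations among measures will be evaluated using Spearman's rank test and General Linear Models, respectively".

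No covariate is named for the Aim 3 or Aim 4 models. The term longitudinal is not defined. Neither a change measure nor a baseline-adjusted post-chemotherapy value is specified. Data Analysis counts p-values below 0.05 as significant, and "no adjustments will be made for multiple comparisons".

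**The concern.** The study's rationale is that chemotherapy disturbs the gut barrier and that the resulting immune priming helps the tumor regress. That process takes place during treatment. The post-chemotherapy draw is the only immune measure taken after it, so readers will look there for a relation between the microbiome and the immune effect of chemotherapy.

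A post-chemotherapy level cannot show that relation by itself. If a microbial measure is correlated with a subset before treatment, and women tend to keep their rank, the same measure will be correlated with the subset afterwards even if it has no bearing on what happened in between. The same holds for the host factors in Aim 4, such as age, BMI and smoking. The pilot is meant to supply parameters for a larger study, so a carried-over correlation could be used for planning as if it were a treatment-period effect.

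The point concerns circulating subsets only. Tumor infiltrates are measured only before treatment and have no second value.

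**Working it through.** **1. The plan's own figure.** Power and Sample Size gives 80% power for Aims 3 and 4 with 20 women, a slope of 0.67 SD per SD and a "two-sided α =0.05 significance level". Take a one-predictor regression and read 0.67 in residual SD units. The noncentrality is 0.67 × √20 = 3.00 on 20 − 2 = 18 degrees of freedom, and power is 80.9%. The stated figure reproduces as a model with no baseline term.

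**2. Inputs for the carry-over check.** The numbers of women come from the documents: 20 (Power and Sample Size) and 40 expected completers (Study Population). Two correlations are assumed, because the documents give neither:
- r0, microbial measure with baseline subset: 0.3 or 0.5
- ρ, baseline subset with post-chemotherapy subset in the same woman: 0.5 or 0.7

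The null is that the microbial measure has no relation to the post value once baseline is known.

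**3. Formula.** Under that null the correlation of the microbial measure with the post-chemotherapy level is r0 × ρ. The numerator of the partial correlation given baseline is r0ρ − r0ρ = 0.

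By Fisher's z, the chance of a significant crude test is roughly Φ(atanh(r0ρ) × √(n − 3) − 1.96), ignoring the far tail. For r0 = 0.5, ρ = 0.7, n = 40: atanh(0.35) = 0.365; 0.365 × √37 = 2.22; Φ(0.26) ≈ 60%.

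**4. Simulation** (bivariate normal, 20,000 runs per cell, crude linear test):

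| r0 | ρ | r0ρ | crude, n=20 | crude, n=40 | baseline in model, either n |
|---|---|---|---|---|---|
| 0.3 | 0.5 | 0.15 | 9% | 15% | 5% |
| 0.3 | 0.7 | 0.21 | 15% | 26% | 5% |
| 0.5 | 0.5 | 0.25 | 19% | 34% | 5% |
| 0.5 | 0.7 | 0.35 | 33% | 62% | 5% |

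The Spearman test that the plan names rejects slightly less often. At r0 = 0.5, separate runs gave 17–18% (ρ = 0.5) and 29–31% (ρ = 0.7) with 20 women, and 31% and 56–57% with 40. At r0 = 0.3 with 40 women it rejected in 14% and 24%. Over the grid this is about 9–31% with 20 women and 14–57% with 40.

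**5. Effect on precision.** Here ρ is taken given the microbial measure. Adding baseline multiplies the variance of the slope by (1 − ρ²)/(1 − r0²), apart from the lost degree of freedom. Power is for 20 women and a slope of 0.67 residual SD, against 80.9% unadjusted:
- r0 = 0, ρ = 0.7: 0.51/1 = 0.51; power 98%.
- r0 = 0.5, ρ = 0.5: 0.75/0.75 = 1.00; power 81%.
- r0 = 0.5, ρ = 0.3: 0.91/0.75 = 1.21; power 73%.
- r0 = 0.67, ρ = 0.5: 0.75/0.551 = 1.36; power 68%.

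Adjustment gains precision when ρ exceeds r0 and loses it when r0 exceeds ρ.

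**6. Is a change score an alternative?** Under the same null, change correlates with the microbial measure at −r0 × √((1 − ρ)/2). For r0 = ρ = 0.5 that is −0.5 × √0.25 = −0.25. The change score is then significant in 19% of runs with 20 women and 35% with 40, through regression to the mean. With two complete draws, a mixed model's time-by-exposure term tests this same quantity.

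**The case against.** The strongest reply is that Aim 3 asks only for associations. It never promises an analysis of change, and its term for immune response also covers infiltrates in tissue taken before treatment, so response may mean response to the tumor rather than to chemotherapy. On that reading a correlation with the post-chemotherapy level is a legitimate estimate, and conditioning on baseline removes part of it. This stands as far as it goes: the rejection rates above are errors only if the result is read as a treatment-period relation. The plan does not say which reading it intends, and its rationale invites the treatment-period one. Reporting both analyses meets the objection.

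Three stronger readings are tempting, and the documents do not support them:
- **That the linear model leaves baseline out.** The models are covariate-adjusted with covariates unnamed, so baseline is unspecified, not excluded. The power figure matches a one-predictor model, but that does not settle what will be fitted. Only for the bivariate Spearman test is the omission definite.
- **That the two draws will be stacked as independent rows.** Nothing says so. Separate analyses at each time fit the text equally well.
- **That omitting baseline always wastes precision.** Step 5 shows that this depends on two correlations the documents do not give, and that it can reverse.

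It is also fair that this is an exploratory pilot and that its stated power is not wrong.

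**Conclusion.** The point holds as a gap in specification with a real consequence for interpretation. As written, the crude post-chemotherapy test cannot separate a relation to the immune response during chemotherapy from one already present before it, and the plan does not commit the adjusted model to doing so. If there is no relation beyond baseline, the crude test is significant in about 9–31% of studies with 20 women and 14–57% with 40, against about 5% with baseline in the model.

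These figures rest on assumed correlations (0.3–0.5 with baseline, 0.5–0.7 within woman), normal data and a baseline measured without error. Measurement error would leave some bias even after adjustment. With no baseline correlation the crude test keeps its 5% level. In an exploratory pilot this is a change that should be made, not one on which the study's validity turns.

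**What to change.** In Data Analysis, Aims 3 and 4, for post-chemotherapy circulating subsets:
- Fit the General Linear Model with the baseline value of the same subset as a named covariate, and use a partial rank correlation given baseline as the Spearman counterpart.
- Report the associations with the baseline subsets separately.
- Label any unadjusted post-chemotherapy correlation as an association with level, not with response to treatment.

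A plain change score, or a mixed model with a time-by-exposure term, should not be offered as equivalent (step 6).

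The cost is a sentence or two of text and one degree of freedom, with no new samples. Precision falls somewhat where the exposure is more strongly correlated with baseline than baseline is with the post value, and improves in the opposite case.
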